### HAD QUESTIONNAIRE

D	A		D	A	
		I feel tense or 'wound up':			I feel as if I am slowed down:
	3	Most of the time	3		Nearly all the time
	2	A lot of the time	2		Very often
	1	From time to time, occasionally	1		Sometimes
	0	Not at all	0		Not at all
		I still enjoy the things I used to enjoy:			I get a sort of frightened feeling like 'butterflies' in the stomach:
0		Definitely as much		0	Not at all
1		Not quite so much		1	Occasionally
2		Only a little		2	Quite Often
3		Hardly at all		3	Very Often
		I get a sort of frightened feeling as if something awful is about to happen:			I have lost interest in my appearance:
	3	Very definitely and quite badly	3		Definitely
	2	Yes, but not too badly	2		I don't take as much care as I should
	1	A little, but it doesn't worry me	1		I may not take quite as much care
	0	Not at all	0		I take just as much care as ever
		I can laugh and see the funny side of things:			I feel restless as I have to be on the move:
0		As much as I always could		3	Very much indeed
1		Not quite so much now		2	Quite a lot
2		Definitely not so much now		1	Not very much
3		Not at all		0	Not at all
		Worrying thoughts go through my mind:			I look forward with enjoyment to things:
	3	A great deal of the time	0		As much as I ever did
	2	A lot of the time	1		Rather less than I used to
	1	From time to time, but not too often	2		Definitely less than I used to
	0	Only occasionally	3		Hardly at all
		I feel cheerful:			I get sudden feelings of panic:
3		Not at all		3	Very often indeed
2		Not often		2	Quite often
1		Sometimes		1	Not very often
0		Most of the time		0	Not at all
		I can sit at ease and feel relaxed:			I can enjoy a good book or radio or TV program:
	0	Definitely	0		Often
	1	Usually	1		Sometimes
	2	Not Often	2		Not often
	3	Not at all	3		Very seldom

Please check you have answered all the questions

#### Scoring:

Total score: Depression (D) \_\_\_\_\_ Anxiety (A) \_\_\_\_\_

**QUESTIONNAIRE HIT**

[figure not shown]
**HIT-6™**  
(VERSION 1.1)

This questionnaire was designed to help you describe and communicate the way you feel and what you cannot do because of headaches.

To complete, please circle one answer for each question.

1	When you have headaches, how often is the pain severe?	Never	Rarely	Sometimes	Very Often	Always
2	How often do headaches limit your ability to do usual daily activities including household work, work, school, or social activities?	Never	Rarely	Sometimes	Very Often	Always
3	When you have a headache, how often do you wish you could lie down?	Never	Rarely	Sometimes	Very Often	Always
4	In the past 4 weeks, how often have you felt too tired to do work or daily activities because of your headaches?	Never	Rarely	Sometimes	Very Often	Always
5	In the past 4 weeks, how often have you felt fed up or irritated because of your headaches?	Never	Rarely	Sometimes	Very Often	Always
6	In the past 4 weeks, how often did headaches limit your ability to concentrate on work or daily activities?	Never	Rarely	Sometimes	Very Often	Always

To score, add points for answers in each column.

Please share your HIT-6 results with your doctor.

**Total Score**

Higher scores indicate greater impact on your life.

Score range is 36-78.

1. STUDY SYNOPSIS

Music therapy has been validated in the management of chronic pain and anxiety disorders. A program of music therapy will be proposed by the CHU Chronic Pain department team from GHSR. The objective of this study is to evaluate the effect of the music in the migraine specific indication.

This study has been designed as a before-after study without control group. It comprises of only one group of patients and all of them will receive the intervention.

The study will measure and compare migraine frequency during the month before inclusion with migraine frequency 3 months after the inclusion.

Intervention being realized under current practice, it was not possible to propose a randomized trial with one arm is treated with music therapy and another one not.

The month before inclusion will serve as reference. Effect of music therapy will be evaluated during 3 months after inclusion, using a period of same duration of the reference one and using the same tools. During the 3 months, patients will be followed every month during a visit realized at Chronic Pain Department of GHSR in order to evaluate if the patient is compliant in completion of migraine diary, uses correctly Music Care and if he is compliant with his program. During the visit, migraine evaluation will be evaluated.

2. OBJECTIVES

2.1. PRIMARY OBJECTIVE

To evaluate the effect of music therapy on migraine frequency, on patients suffering from episodic migraines and followed in chronic pain department of the CHU Sud Reunion.

2.2. SECONDARY OBJECTIVES

- To evaluate the effect of music therapy on migraine intensity, duration, and acute treatment administration.
- To evaluate the effect of music therapy on emotional effect (HAD score) and functional impact (HIT-6 score).

3. EVALUATION CRITERIA

Primary and secondary endpoints are defined according to the last recommendations related to the evaluation of prophylactic migraine treatment of ANAES October 2002: « Treatment is considered as efficient if crisis frequency is reduced of at least 50 %. It is also important to consider the reduction of medication consumption, intensity and duration of crisis. Evaluation is done after 3 months. ». The methodology is consistent with guidelines of International Headache Society for clinical research on migraine.

3.1. PRIMARY ENDPOINT

Reduction of migraine crisis frequency of at least 50% after 3 months of treatment.

The studied variable is the monthly frequency of migraine crisis. Data collection is done using a migraine agenda (annex 1 of protocol), starting the month before inclusion and music therapy initiation. This agenda should then be completed usually during study period under music therapy. During each monthly visit, a control will be done by the intern of general medicine associated to the study.

The primary endpoint is obtained using the difference between mean crisis frequency during the month before music therapy initiation and the one obtained during the 3rd month of treatment. A reduction of at least 50% at month 3 is considered as music therapy efficacy on episodic migraine prevention.

3.2. SECONDARY ENDPOINTS

- Reduction of crisis intensity and duration, as well as medication consumption.

Crisis intensity (mild, moderate, severe), duration in hour, and the number of treatments taken are collected in the migraine agenda (annex 1 of protocol) filled by the patient. These variables will be compared between the month before music therapy initiation and the 3rd month of treatment.

- Reduction of functional and emotional impact.

Questionnaires HAD and HIT (annex 2 of protocol) will be completed with the investigator during the inclusion visit before initiation of music therapy, and at Month 3 visit.

- Questionnaire HAD to evaluate emotional impact (national reference HAS « chronic pain: recognize chronic pain syndrome, evaluate it and guide the patient »)
- Questionnaire HIT to evaluate functional impact (guideline of the International Headache society)

4. STUDY POPULATION

Intent-to-treat (ITT) Population: all the patients with at least on music session and sufficient completion of migraine diary to have evaluation at Month 3 of the primary endpoint.

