## 7.6. INCLUSION VISIT

During this visit, a complete information on objectives and course of the study is provided to the patient. Informed consent is collected by the algologist investigator of the study.

Diagnosis questionnaire, and HAD and HIT questionnaires HAD et HIT are completed with the investigator. Migraine agenda to be filled during the next 3 months is provided to the patient.

A training to *Music care*, music therapy software, is realized by the study responsible. Details on methodology, objectives of the technique, as well as the optimal conditions of use are given to the patient. During this visit, the first music session is done at the hospital under medical control. A questionnaire is filled in order to have a better knowledge of migraine patient about music preferences likely to bring him to relaxation.

A secure account is created to allow patients to have a free internet access and use *Music care* during the study.

At the end of this visit, the patient should be able to use at home by himself the software and to realize music therapy sessions using *Music care*.

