## 7.7. FOLLOW-UP VISITS

Follow-up visits will be monthly done by the investigator, at Month 1, Month 2 and Month 3 after inclusion. During these visits, checks will be done regarding agenda migraine completion, patient motivation will be evaluated, and the number of music sessions done will be collected.

Impressions and feeling of the patient regarding music sessions will be collected.

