#### Analysis of secondary endpoints

Quantitative variables measured before music therapy will be compared with the ones collected after music therapy using the same statistical method as for primary endpoint.

Qualitative variables (proportions) measured before music therapy will be compared with the ones collected after music therapy using McNemar Chi test.

All the tests will be realized with SAS 9.2 software with  $\alpha = 5\%$ . A statistical analysis plan will be prepared and will detailed the different analyses.

---

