### **10.2. SOURCE DATA**

Source data or document is defined as any original document which allow to demonstrate the existence, or the accuracy of a data collected during the research.

Source documents come from:

- Case Report Form
- Questionnaires filled during inclusion visit: diagnosis, HAD and HIT impact
- Migraine diary, filled the month before inclusion and during 3 months under intervention
- End of study questionnaires: HAD and HIT

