## **11. QUALITY CONTROL**

### **11.1. INFORMATION FOR DATA COLLECTION**

All information required by the protocol shall be recorded on the observation books and an explanation shall be provided for each missing data. Data should be collected as they are obtained and transcribed into these books in a neat and legible manner.

Incorrect data found on the observation books will be clearly crossed out and the new data will be copied, next to the crossed-out information, accompanied by initials, the date and possibly justification by the person who is directing and monitoring the research or the authorized person who made the correction.

Data are collected on a paper CRF.

The data to be collected directly in the CRF will be:

- age, sex
- migraine diagnosis according to International Headache Society criteria
- number of days with headache per month
- duration and intensity of crises
- headache treatment medication per month
- HAD and HIT

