5.2. STATISTICAL METHODS USED

All the tests will be realized with SAS 9.2 software with $\alpha = 5\%$.

Baseline characteristics

Baseline characteristics will be summarized. Qualitative variables will be described using number of patients, percentage and 95% confidence interval (IC95%). Quantitative variables will be described as number of patients, mean, standard deviation, confidence interval of the mean, median, Q1, Q3, minimum and maximum.

Analysis of primary endpoint

Monthly mean number of migraine crisis before music therapy will be compared to the one obtained at Month 3 using Wilcoxon signed rank test for paired (dependent samples). The analysis will be performed in intent-to-treat.

Analysis of secondary endpoints

Quantitative variables measured before music therapy will be compared with the ones collected after music therapy using the same statistical method as for primary endpoint.

Qualitative variables (proportions) measured before music therapy will be compared with the ones collected after music therapy using McNemar Chi² test.

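### SAP section 4 labels a Month 3 diary-evaluable set intent-to-treat, with no diary threshold and no analysis of excluded patients, so outcome-related diary loss could bias the uncontrolled reduction in either direction

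*SAP*

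**What the plan says.** On the primary analysis, SAP 5.2 states: "The analysis will be performed in intent-to-treat". Protocol 9.2 says the same, does not define the term, and defers the detail: "A statistical analysis plan will be prepared and will detailed the different analyses".

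SAP section 4 supplies the only definition. A patient belongs to the intent-to-treat population after at least one music session and with "sufficient completion of migraine diary to have evaluation at Month 3 of the primary endpoint". Neither document defines another population.

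The result is read against a fixed line in SAP 3.1: "A reduction of at least 50% at month 3 is considered as music therapy efficacy on episodic migraine prevention". SAP section 1 describes a single group compared with its own reference month.

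Other relevant text in the protocol:
- Section 7.6, on the inclusion visit: "During this visit, the first music session is done at the hospital under medical control".
- Section 7.7, on the monthly visits: "checks will be done regarding agenda migraine completion".
- Section 10.2 lists among the source documents: "Migraine diary, filled the month before inclusion and during 3 months under intervention".
- Section 11.1 asks for a reason for each missing item and lists as a CRF item: "number of days with headache per month".

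**The concern.** In ordinary usage an intent-to-treat analysis keeps patients whether or not their outcome was obtained. The SAP set depends on whether the outcome was obtained. Because the first session takes place at the inclusion visit, the session condition removes almost nobody, and the diary condition does nearly all the excluding.

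Two things needed to apply that condition are absent. Sufficient completion has no minimum number of days and no rule for gaps, so the decision on who is in the set is left open. For a patient judged insufficient there is no imputation, no alternative analysis and no sensitivity analysis. The monthly checks and the recorded reasons may reduce or document loss, but they do not say how to analyse it.

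At stake is the single before-after estimate. If patients who stop the diary did worse than the rest, the evaluable set overstates the reduction; if they did better, it understates it. A result close to 50% could fall on the other side of the line once all included patients are counted, and a reader told only that the analysis was intent-to-treat would not know that patients had been left out.

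**Working it through.** **The plan's own figure.** SAP 5.1 gives a mean of 8 crises per month, SD 4, a 50% reduction (4 crises), 90% power, alpha 5% and 20 patients. It gives no SD of change, no correlation and no sidedness. With correlation 0 the SD of change is √(4² + 4²) = 5.66, and the normal formula gives

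n = [5.66 × (1.960 + 1.282) / 4]² = 21.01, so 22 two-sided; the one-sided value is 17.13, so 18.

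Both are within 2 of 20, so the figure is reproduced approximately, though not uniquely. No allowance for exclusions is stated. The point below does not depend on this figure.

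**Effect of exclusions on the estimate.** I read the 50% criterion as a reduction in the group mean, as SAP 3.1 and 5.1 describe it. Assumptions:
- 20 patients are included and k of them are excluded for an insufficient diary. The documents give no rate, so k is taken as 1, 2, 4 and 6.
- Excluded and evaluable patients have equal baseline means.
- The evaluable set shows exactly 50%, and the excluded patients changed by a reduction of x%.

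All-patient reduction = [(20 − k) × 50 + k × x] / 20

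| k | x = 0 | x = 50 | x = 75 |
|---|---|---|---|
| 1 | 47.5% | 50% | 51.25% |
| 2 | 45% | 50% | 52.5% |
| 4 | 40% | 50% | 55% |
| 6 | 35% | 50% | 57.5% |

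For k = 4: (16 × 50 + 4 × 0) / 20 = 40, and (16 × 50 + 4 × 75) / 20 = 55. With k = 0 the two estimates are the same.

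**The reverse question.** For the all-patient reduction to be 50%, the evaluable set must show (1000 − k × x) / (20 − k):

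| k | x = 0 | x = 75 |
|---|---|---|
| 2 | 55.6% | 47.2% |
| 4 | 62.5% | 43.8% |
| 6 | 71.4% | 39.3% |

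**Setting excluded patients to no change is not a floor.** If four excluded patients had worsened by 25%, the all-patient figure would be (16 × 50 − 4 × 25) / 20 = 35%, below the 40% from no change. It is a useful sensitivity value, not a bound.

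**Effect on power.** Two-sided paired t-test, difference 4, as an approximation to the planned Wilcoxon test:

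| Evaluable patients | SD of change 4 (correlation 0.5) | SD of change 5.66 (correlation 0) |
|---|---|---|
| 20 | 98.9% | 85.1% |
| 16 | 96.2% | 75.3% |
| 14 | 93.2% | 68.7% |

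Whether exclusions cost much power depends on an SD that the documents do not give.

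**The case against.** **The documents do not contradict each other.** The protocol leaves its term undefined and defers to the SAP, which states its restriction openly and uses the term consistently. In a single-arm study the usual meaning of intent-to-treat is a convention. This stands: a reader might infer a conflict between documents or an intention to conceal, and neither is supported. The definition still conditions on the outcome being available, and no other analysis makes up for it.

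**The size is assumed.** Diary completion is checked at inclusion and at every monthly visit, and loss may be small or nil. This stands in full. The tables show what could happen at given rates, not what will.

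**The direction is unknown.** A reader might infer that the reported reduction will be inflated. Nothing in the documents says who would stop the diary.

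**Non-adherent patients are not removed.** A reader might take the set to contain only patients who kept up the music. SAP section 4 does not say so: someone who stops the sessions but keeps the diary stays in. The defect concerns lost diaries only.

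**Fewer than 20 evaluable patients need not be serious.** Protocol 5.3 speaks of about 20 patients, and with an SD of change of 4, 14 evaluable patients still give 93.2% power. The documents do not support a claim that exclusions leave the study underpowered.

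**A controlled trial can also suffer selective loss.** True, and counting all included patients would not turn a before-after comparison into a causal one. The absence of a control arm matters here only because one estimate, read against one line, carries the whole claim.

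**Conclusion.** The point holds. The plan promises an intent-to-treat primary analysis and delivers a Month 3 diary-evaluable one, with no completeness threshold and nothing planned for the patients left out. If diary loss is related to outcome, the reduction read against 50% can be biased upwards or downwards.

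The defect is plain on the text; its size is unknown. With 4 of 20 excluded, equal baseline means and excluded patients ranging from no change to a 75% improvement, an observed 50% corresponds to between 40% and 55% in all included patients. A single exclusion moves it to between 47.5% and 51.25%. With no exclusions, or with excluded patients who improved equally, nothing changes. The documents support no claim about the likely direction, the number lost, or a definite loss of power.

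**What to change.** In the SAP, before data are seen:

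1. Define intent-to-treat as all included patients with at least one session and a reference-month diary. These conditions are met by the end of the inclusion visit, so they do not depend on the Month 3 outcome. Rename the present set *Month 3 evaluable*.
2. Fix one minimum number of diary days, with a proration rule, for every month used: the reference month and Months 1 to 3. Use the same count as the primary endpoint, after reconciling crises (SAP 3.1) with days with migraine (protocol 4.1, final evaluation) and headache days (protocol 11.1).
3. Keep the Wilcoxon test on the evaluable set and describe it as such. Pre-specify one all-included estimate of the Month 3 reduction that uses the Month 1 and Month 2 diaries. A repeated-measures mixed model is one suitable example; its covariance structure and interval method are for the sponsor to choose and state. Such a model relies on loss being explained by the recorded diaries, so add a sensitivity estimate with excluded patients set to no change.
4. State in advance that a claim of at least 50% is read on the all-included estimate, with the evaluable estimate beside it. Report the number excluded, with reasons.
5. Record the change against protocol 9.2, which ties the Wilcoxon test to intent-to-treat, and check under protocol 12.2 whether it is substantial.

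The cost is SAP text and a little more analysis on about 20 patients. The diaries for all months are already source documents, so patients provide nothing new. If crises are kept as the count, monthly crisis counts may have to be extracted from the diaries, because the CRF list names headache days. The headline figure may be less favourable. The 50% criterion itself does not change.

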5. STATISTICAL METHODS

5.1. SAMPLE SIZE CALCULATION

Primary endpoint is the reduction on migraine crisis frequency before and after music therapy.

In the population of patients corresponding to inclusion criteria, mean number of migraine crisis per month can be estimated to 8 (standard deviation = 4) before intervention.

A reduction clinically significant would be a reduction of at least 50% of mean monthly number of migraine crisis after 3 months of care.

Under these conditions, 20 patients are needed to have this difference of 50% with a statistical power of 90% and an alpha equal to 5%.

5.2. STATISTICAL METHODS USED

All the tests will be realized with SAS 9.2 software with $\alpha = 5\%$.

Baseline characteristics

Baseline characteristics will be summarized. Qualitative variables will be described using number of patients, percentage and 95% confidence interval (IC95%). Quantitative variables will be described as number of patients, mean, standard deviation, confidence interval of the mean, median, Q1, Q3, minimum and maximum.

Analysis of primary endpoint

Monthly mean number of migraine crisis before music therapy will be compared to the one obtained at Month 3 using Wilcoxon signed rank test for paired (dependent samples). The analysis will be performed in intent-to-treat.

Analysis of secondary endpoints

Quantitative variables measured before music therapy will be compared with the ones collected after music therapy using the same statistical method as for primary endpoint.

Qualitative variables (proportions) measured before music therapy will be compared with the ones collected after music therapy using McNemar Chi² test.
